6.1.6 Discontinuation of Therapy

The Investigator will withdraw a patient whenever continued participation is no longer in the patient's best interests. Reasons for withdrawing a patient include, but are not limited to, disease progression inside the PTV or at distant sites at any point, the occurrence of an adverse event or a concurrent illness, excessive delay in protocol treatment (greater than 4 weeks), a patient's request to end participation, a patient's non-compliance or simply significant uncertainty on the part of the Investigator that continued participation is prudent. There may also be administrative reasons to terminate participation, such as concern about a patient's compliance with the prescribed treatment regimen.

Table 6.1 Schedule of Study Procedures and Assessments

All evaluations have a window of +/- 3 days unless noted otherwise below.

Study Week/Visit Week	Period/ Procedure		Screening		Induction		End of Induction (Re-Evaluation)		Concurrent Therapy					End of Treatment	Follow-up visits ¹
	-28 to -1	-14 to -1	5	9	13-14	15	16	17	18	19	20	21	29-33		
Informed consent	X														
Assignment of patient ID number		X													
Baseline conditions		X													
AE assessment ²		X	X	X	X	X	X	X	X	X	X	X	X	X	
Concomitant medications	X		X	X	X	X	X	X	X	X	X	X	X	X	
Treatment/Drug Administration															
Vismodegib			Daily (150 mg/day)												
Radiation Therapy			Daily (5 fractions/week)												
Clinical procedures															
Physical exam ³		X	X	X	X	X	X	X	X	X	X	X	X	X	
Vital signs ⁴		X	X	X	X								X	X	
Medical history	X														
Disease assessment	X				X								X	X	
Performance status		X	X	X	X								X	X	
Biopsy	X ⁵														
Skindex-16 Survey		X	X	X	X								X	X	
Digital photographs ⁵		X			X								X	X	
Tumor measurements ⁵		X			X								X	X	
Fine Needle Biopsy ⁶		X													
Dental evaluation ⁶		X													
Laboratory procedures															
Hematology ⁷		X	X	X	X				X				X	X	
Blood chemistry ⁸		X	X	X	X				X				X	X	

Table 6.1 Schedule of Study Procedures and Assessments

All evaluations have a window of +/- 3 days unless noted otherwise below.

Period/ Procedure	Screening		Induction		End of Induction (Re-Evaluation)		Concurrent Therapy						End of Treatment	Follow-up visits ¹
	-28 to -1	-14 to -1	5	9	13-14	15	16	17	18	19	20	21	29-33	
Pregnancy test (HCG)		X ¹¹	X	X	X				X				X	X ¹¹
Urinalysis		X							X					
Imaging procedures														
Imaging (CT or MRI) ^{6,9}	X				X								X	X
Chest x-ray, CT Chest, or PET/CT ^{6,10}	X				X								X	X

- Follow-up visits will occur at 3, 6, & 12 months (+/- 2 weeks) post EOT. Patients with documented disease progression within the irradiated PTV will be removed from study treatment. Survival follow-up information may be collected via telephone calls and/or at clinic visits every 3 months for 12 months.
- The reporting period for adverse events (AEs) and serious adverse events (SAEs) will begin at the time of enrollment and continues until 90 days after the last dose of vismodegib. During screening, only SAEs related to protocol-mandated procedures should be reported. At the end of the study period, any patient with an ongoing AE or SAE will be followed until the event resolves, the investigator assesses the event as stable, or the patient is lost to follow-up.
- A complete physical exam includes evaluation of the head, eyes, ears, nose and throat; cardiovascular, dermatological, musculoskeletal, respiratory, gastrointestinal, and neurological systems. Exam includes height (at screening only) and weight.
- Vital signs include pulse, systolic and diastolic blood pressure while the patient is in a seated position, respiratory rate, and temperature.
- For externally visible tumors. Can be done up to 180 days prior to day 1. Additional biopsy after screening will only be to confirm progression.
- Dental evaluation, fine needle biopsy, Brain MRI, and PET/CT are highly recommended but not required at screening.
- Hematology consists of hemoglobin, hematocrit, platelet count, red blood cell (RBC) count, white blood cell (WBC) count, and percent or absolute differential count (neutrophils, eosinophils, lymphocytes, monocytes, basophils, and other cells).
- Serum chemistry includes glucose, blood urea nitrogen (BUN), creatinine, sodium, potassium, magnesium, chloride, bicarbonate (if routinely performed on venous blood samples), calcium, total protein, albumin, total bilirubin, alkaline phosphatase, AST, and ALT, and as clinically indicated; LDH, and phosphorus
- The CT scan with contrast or an MRI with gadolinium must be done unless medically contraindicated. The MRI or CT scan must encompass the skull base and/or upper mediastinum if those areas are involved. If locally advanced BCC lesions with a RECIST-measurable component are identified, the same imaging modality used at baseline must be used throughout the study.
- Locally advanced BCC patients should have a CT of the chest and abdomen at baseline to assess for possible metastatic disease or other significant abnormalities. Abdominal imaging must cover the liver and adrenal glands; therefore, separate abdominal imaging is not required if these areas are covered by a chest CT scan. If this scan shows no significant findings at baseline, it does not need to be repeated for tumor assessment.
- No need to repeat Week 1 if screening test is within 1 week prior. Pregnancy testing at 3 months and 6 months Follow-Up visits only.

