6.1.4 Post-treatment/Follow Up Visits

Patients will be followed at 3, 6, and 12 months (+/- 2 weeks) after the End of Treatment visit or until disease progression. The following procedures will be performed at the Follow-Up Visit(s):

- Evaluation of clinical response or deterioration
- Physical examination including weight
- Vital signs
- Performance Status
- Evaluation of adverse events
- Concomitant medications
- Skindex-16 survey
- Laboratory assessments
 - Hematology

- Serum chemistries
- Urine or serum pregnancy tests - if a woman of childbearing age – at 3 and 6 month visits only
- Disease assessment
- Imaging (CT or MRI) of head and neck for tumor assessment
- CT chest or chest x-ray – if clinically indicated
- For externally visible tumors
 - Bidimensional measurements of externally visible tumor dimension
 - Digital photography of target lesion(s)
 - Description of the lesion
 - Tumor biopsy - to confirm progression

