6.1.5 Long Term/Survival Follow-up Procedures

The study team will follow patients for survival outcome via telephone calls or medical record requests approximately every 3 months for 12 months, until death or loss to follow-up, whichever occurs first. Additional, survival follow-up information may be collected via telephone calls and/or at clinic visits every 3 months for 12 months. Follow-up may consist of at least a telephone contact with the patient, a family member, or physician to inquire about the patient's survival status.

If/when a subject begins a new type of non-protocol treatment for laBCC or mBCC, long-term follow up may cease. Subjects will continue to be followed if they have not recurred local-regionally within the original treated PTV. If they have a BCC in a non-treated separate location, or if metastatic disease occurs, subjects will continue to be followed for the local-regional disease control outcomes. Subjects would be taken off protocol if they have any form of non-protocol treatment affecting the primary local or nodal site that was originally treated or if they receive vismodegib or other Hedgehog inhibitor or chemotherapy outside of original protocol parameters. Patients off study protocol who need to have vismodegib will not have drug provided by the study.

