8.2 Study Endpoints

Primary Endpoint:

- The proportion of patients with local-regional control at 12 months from protocol therapy completion, defined as complete or partial response, with absence of PD (see section 7.2) within the irradiated PTV.

Secondary Endpoints:

- Estimate of the probability of PFS and OS 12 months after protocol therapy completion. PFS is measured until disease recurrence or death due to any cause, whichever occurs first.
- Number and attribution of all adverse events (including vital signs, physical findings, and clinical laboratory results, CTCAE, v 4.0) in patients who receive any amount of study drug and radiation therapy.
- For each toxicity, the maximum occurring grade will be tabulated for each patient. The results will be summarized by toxicities observed during vismodegib treatment alone, during concurrent vismodegib with radiation therapy, for 3 months immediately following the completion of protocol therapy and for up to 12 months after completion of protocol therapy. The focus will be on the proportion of patients experiencing \geq grade 3 toxicity during each of these intervals.
- Proportion of patients experiencing Grade 4-5 adverse events assessed to be definitely, probably, or possibly related to the induction or concurrent treatment components of the protocol regimen (that is not definitely related to disease progression).
- Proportion of patients discontinuing treatment due to toxicity during the concurrent administration of vismodegib and radiation therapy. For this endpoint, discontinuation is defined as $<$ 75% of planned radiation therapy delivered.
- Response rate per RECIST criteria in patients who complete initial combined therapy of the primary site and regionally involved areas in subjects with measurable disease prior to initiation of therapy at 3 months after completion of protocol therapy.
- Proportion of patients with a decrease of BCC within the irradiated PTV after completing all protocol therapy to estimate clinical response to vismodegib and radiation therapy.

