8.3 Determination of Sample Size and Accrual Rate

8.3.1 Sample Size and Power Estimate

The sample size for this single-arm phase II study is based upon the anticipated degree of improvement in the primary clinical hypothesis (i.e. local-regional control rate) at 12 months after completing all protocol treatment. The null hypothesis is that 60% of patients treated may achieve local-regional control after treatment on the study. Patients treated for advanced-stage

nonmelanomatous skin cancers typically achieve 50-60% local-regional control with radiation therapy alone. The alternative hypothesis is that 80% of the patients will obtain local-regional control at 12 months from the end of protocol therapy. This goal for local-regional control is justifiable as the current study includes radiation therapy, which is known to be effective against advanced BCC, in combination with vismodegib, also known to have high efficacy against BCC when administered alone.

Sample Size Justification: With accrual of 24 evaluable patients, this test will have 81% power to detect an increase in the overall proportion of patients achieving local-regional control assuming a directional level of significance of 0.10 based upon a one sample exact binomial test. It is anticipated that accrual will be completed in 12-18 months, with each patient treated for approximately 5.5 months and then followed for 12 months after completing protocol therapy. The total study duration is expected to be about 3 years.

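### Section 6.1.4 can end the visits that measure the primary outcome at progression outside the PTV, contrary to Section 6.1.5, and Section 8.5 does not say how such a patient is counted

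*Combined protocol and SAP*

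**What the plan says.** **Endpoint.** Section 8.2 defines the primary endpoint as "The proportion of patients with local-regional control at 12 months from protocol therapy completion, defined as complete or partial response, with absence of PD", and confines it to the treated PTV. Section 8.5.1 defines failure in the same terms, as loss of control inside the treated PTV during the 12-month follow-up.

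**Text that can end assessment.**
- Section 6.1.4 sets visits at 3, 6 and 12 months "after the End of Treatment visit or until disease progression". These visits carry the head-and-neck CT or MRI, the tumor measurements and the photographs. The progression that ends them is not restricted to the PTV.
- Section 6.1.6 lists "disease progression inside the PTV or at distant sites at any point" among the reasons to withdraw a patient. Its heading refers to therapy; its text refers to participation.

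**Text that continues assessment.**
- Section 6.1.5 provides that, with a BCC in a separate untreated location or with metastasis, "subjects will continue to be followed for the local-regional disease control outcomes".
- Section 3.5 follows patients for 12 months after therapy or until death.
- Section 7.1 refers patients with distant metastases to Section 6.1.5 for possible further follow-up.
- The follow-up footnote to Table 6.1 lists the three visits with no stop at progression, and ties removal from study treatment to in-PTV progression.

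**Missing outcomes.** Sections 8.5 and 8.5.1 give one rule: a patient removed before 75% of radiotherapy without a documented complete or partial response counts as a local-regional failure.

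**The concern.** The endpoint can still be observed after a distant metastasis or a tumor elsewhere on the skin, because it asks only about the PTV. Section 6.1.5 recognises this. Section 6.1.4, which schedules the assessments needed, does not. A site that follows it literally stops imaging the PTV once disease appears elsewhere.

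Such a patient falls into a gap. Having completed radiotherapy, the patient is in the efficacy population, is not replaced under Section 8.3.2, and is not covered by the 75% rule. Out-of-PTV progression alone is not failure under Section 8.5.1, but without a 12-month assessment control is not shown either. Whoever analyses the trial would have to choose how to count the patient after seeing the data. With 24 patients and a single cut-off, that choice matters.

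**Working it through.** **Do the passages conflict?** For distant metastasis they do. Section 7.1 counts a new distant metastasis as progressive disease unless biopsy shows otherwise, so Section 6.1.4 ends the visits while Section 6.1.5 continues follow-up. For a new BCC at a separate untreated site the conflict is less certain. Sections 7.1 and 7.2.1.4 tie new-lesion progression to the PTV, so a site might or might not regard that lesion as the event that ends the visits.

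**Does Section 6.1.5 supply the assessment?** Not by itself. It describes telephone calls, record requests and optional clinic contact, and it schedules no imaging. Response within the PTV needs the Section 6.1.4 procedures. Section 7.1 also makes submission of data voluntary once a patient has progressed and been removed from study.

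**Inputs (Section 8.3.1).**
- Null rate: "The null hypothesis is that 60% of patients treated may achieve local-regional control after treatment on the study", so p0 = 0.60.
- Alternative: "The alternative hypothesis is that 80% of the patients will obtain local-regional control at 12 months from the end of protocol therapy", so p1 = 0.80.
- Size and power: "With accrual of 24 evaluable patients, this test will have 81% power".
- Test: "assuming a directional level of significance of 0.10 based upon a one sample exact binomial test".
- Number k of patients who complete radiotherapy, progress only outside the PTV and have no 12-month in-PTV assessment: not in the documents; assumed 0 to 4.

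**Reproducing the plan's figure.** For X ~ Binomial(n, p), P(X ≥ r) = Σ from x = r to n of C(n, x) p^x (1 − p)^(n − x). With n = 24:
- r = 17: alpha 0.192, too large.
- r = 18: alpha 0.096, power 0.811.
- r = 19: alpha 0.040, power 0.656.

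The cut-off is 18 of 24, and the stated 81% is reproduced.

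**Effect of the counting rule.** Hold k fixed and let the other 24 − k patients follow the binomial model.
- All k counted as failures: 18 controlled patients are needed among 24 − k. Power = P(X ≥ 18), n = 24 − k, p = 0.80.
- All k counted as controlled: 18 − k are needed among 24 − k. Alpha = P(X ≥ 18 − k), n = 24 − k, p = 0.60.
- All k excluded: the smallest cut-off with alpha at most 0.10 is found again for n = 24 − k.

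| k | Power, counted as failures | Alpha, counted as controlled | Excluded: cut-off, alpha, power |
|---|---|---|---|
| 0 | 0.811 | 0.096 | 18/24, 0.096, 0.811 |
| 1 | 0.695 | 0.124 | 18/23, 0.054, 0.695 |
| 2 | 0.543 | 0.158 | 17/22, 0.072, 0.733 |
| 3 | 0.370 | 0.200 | 16/21, 0.096, 0.769 |
| 4 | 0.206 | 0.250 | 16/20, 0.051, 0.630 |

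One such patient is enough to take alpha above 0.10 or power below 0.70, depending on the rule chosen.

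**The case against.** The strongest reply is that the protocol already answers the question. Section 6.1.5 deals with exactly this patient and says follow-up continues. Sections 3.5 and 7.1 and the Table 6.1 footnote point the same way, and a specific provision normally prevails over a general one. This stands in part: the outcome could be lost, but the documents do not make the loss certain.

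A reader might also infer that Section 6.1.6 ends follow-up at any progression. The text does not support that. The section is headed as discontinuation of therapy, does not mention follow-up visits, and names only in-PTV or distant progression in a list that is not exhaustive. Because it speaks of ending participation it is ambiguous, and no more than that. The unqualified stop is in Section 6.1.4.

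The scope is limited as well. Patients who progress during induction leave before radiotherapy (Section 6.1.2.2), outside the Section 8.5.1 efficacy population. Patients removed before 75% of radiotherapy without a documented response already count as failures. What remains is mainly out-of-PTV progression after radiotherapy.

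Finally, a single example can mislead. With two affected patients, 18/24 gives p = 0.096 and 16/24 gives p = 0.328, but 18 is exactly the cut-off. The decision changes only if the count with both scored as controlled is 18 or 19: from 20 it falls to 18 and still rejects, and from 17 it fails either way. That is why the table gives a range of operating characteristics.

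**Conclusion.** The point holds as an internal inconsistency that can cost primary-outcome data, together with a missing analysis rule. It is not an error in the design calculation: the sample size and power are correct as stated, and they are unchanged if all 24 patients are assessed in the PTV at 12 months.

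The tabulated effects rest on an assumed k of 0 to 4. They also take the two extreme scorings, with every affected patient counted the same way whatever the true status, and the remaining patients at exactly the null or alternative rate. They bound the effect of the unstated rule and do not predict what will happen.

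A reader might go further and conclude that patients with out-of-PTV progression are bound to lack the primary outcome, or that the plan scores them as failures. Neither follows. Sections 3.5, 6.1.5 and 7.1 provide for continued follow-up, and Section 8.5.1 confines failure to the PTV.

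**What to change.** 1. **Section 6.1.4:** limit the stop to progression within the irradiated PTV.
2. **Section 6.1.6:** separate the end of study treatment from the end of follow-up, leaving the grounds for stopping treatment as they are.
3. **Sections 6.1.4 and 6.1.5:** state that the planned 3, 6 and 12-month in-PTV assessments, including imaging, continue after distant or other out-of-PTV progression, as 6.1.5 intends.
4. **Section 8.5:** state how a patient without a 12-month in-PTV assessment is counted in the primary analysis, with a sensitivity analysis counting such patients the other way. The rule must cover patients taken off protocol under Section 6.1.5 for non-protocol treatment, such as a Hedgehog inhibitor or chemotherapy. Patients with metastases may well leave by that route, and items 1 to 3 do not close it.

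These are text changes. The visits are already scheduled, so the cost is a few follow-up visits kept that would otherwise be dropped. Sample size and cut-off do not change.

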Duration of Therapy	Patients will receive treatment for approximately 21 weeks.
Duration of Follow up	Follow-up visits will occur at 3, 6, & 12 months (+/- 2 weeks) post End of Treatment visit. Survival follow-up information may be collected via telephone calls and/or at clinic visits every 3 months for 12 months.
Duration of study	The study will reach completion 3-4 years from the time the study opens to accrual.
Study Drugs	Vismodegib capsules (150 mg QD PO) will be taken orally (whole). Patients will be instructed to swallow one capsule once a day (preferably at the same time each day) 7 days/week, with or without food, with about 1 cup (240 mL) of water. Capsules must be swallowed whole; they must not be opened, chewed, broken, or crushed under any circumstances.
Safety Assessments	
The study will use the CTCAE v 4.0 for reporting of non-hematologic adverse events and modified criteria for hematologic adverse events. Safety assessments will consist of monitoring and reporting adverse events (AEs) and serious adverse events (SAEs) that are considered related to vismodegib, all events of death, and any study specific issue of concern.
 
The study period during which all AEs and SAEs must be reported begins after informed consent is obtained and initiation of study treatment and ends 12 months following the last administration of study treatment or study discontinuation/termination, whichever is earlier.

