3.5 Duration of Follow Up

Patients will be followed for 12 months after completion of all protocol therapy, or until death, whichever occurs first. Patients removed from study for unacceptable treatment related adverse event(s) will be followed until resolution or stabilization of all treatment related adverse events to Grade 2 or lower.

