7.4 Evaluation of Safety

Analyses will be performed for all patients having received at least one dose of study drug. The study will use the CTCAE v4.0 for reporting of non-hematologic adverse events and modified criteria for hematologic adverse events. Safety assessments will consist of monitoring and reporting adverse events (AEs) and serious adverse events (SAEs) that are considered related to vismodegib, all events of death, and any study specific issue of concern.

The Principal Investigator at the UCSF Coordinating Center will hold the role of Study Chair. The Study Chair is responsible for the overall conduct of the study and for monitoring its safety and progress at all participating sites. The Study Chair is responsible for ensuring that all AEs and SAEs that are observed or reported during the study, are collected and reported to the FDA, appropriate IRB(s), and Genentech, Inc. in accordance with CFR 312.32 (IND Safety Reports).

The study period during which all AEs and SAEs must be reported begins after informed consent is obtained and initiation of study treatment and ends 1 year following the last administration of study treatment or study discontinuation/termination, whichever is earlier. After this period, investigators should only report SAEs that are attributed to prior study treatment.

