8.1 Study Design

This is a single arm, multi-center, phase II study evaluating the safety and efficacy of treating locally advanced and metastatic BCC patients with vismodegib alone followed by concurrent vismodegib with radiation therapy for a total of 21 weeks. After completing protocol therapy patients will be followed for 12 months. The primary efficacy study outcome measure is the proportion of patients with local-regional control at 12 months after completing protocol therapy.

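### Table 6.1 stops AE reporting 90 days after the last vismodegib dose, while the Abstract, section 7.4 and the toxicity analysis run to 12 months

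*Combined protocol and SAP*

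**What the plan says.** **End of the window.** The AE footnote to Table 6.1 says the period for AEs and SAEs "continues until 90 days after the last dose of vismodegib". The Abstract (Safety Assessments) says it "ends 12 months following the last administration of study treatment or study discontinuation/termination, whichever is earlier". Section 7.4 says it "ends 1 year following the last administration of study treatment or study discontinuation/termination, whichever is earlier" and adds: "After this period, investigators should only report SAEs that are attributed to prior study treatment".

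**Start of the window.** The footnote starts at enrollment and limits screening reports to SAEs related to protocol-mandated procedures. The Abstract and 7.4 start only once consent has been given and study treatment has begun.

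**What the analysis uses.** Section 3.5: "Patients will be followed for 12 months after completion of all protocol therapy, or until death, whichever occurs first". Section 8.1: "After completing protocol therapy patients will be followed for 12 months". Section 2.3.2 extends its AE endpoints over the follow-up period. Sections 8.2 and 8.5 tabulate maximum grade in four stages: drug alone, drug with radiation, the first 3 months after therapy, and then up to 12 months after therapy.

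**When AEs are assessed.** Section 6.1.4 lists AE evaluation at the 3-, 6- and 12-month follow-up visits, and the AE row of Table 6.1 is marked in the follow-up column. These visits are counted from the End of Treatment visit, which 6.1.3 places 8 to 12 weeks after the last dose.

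**Grade entered in OnCore.** Section 7.6 and Appendix 9 name grade 3 to 5 events. Section 7.8 says all AEs are entered, but refers back to the preceding text. Section 9.6 puts all study data in OnCore.

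**The concern.** The two end points cannot both be the rule, and the documents give no order of precedence between a schedule footnote and section 7.4. The footnote also disagrees with its own table, which marks AE assessment at follow-up visits that the footnote's window never reaches.

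At stake is the fourth toxicity stage and the follow-up part of the AE endpoints in 2.3.2. A site working to the footnote has no duty to report an event that begins after day 90, whatever its grade. If sites differ, a late event that did not occur cannot be told apart from one that was not reported. Section 4.2 says that wound-healing effects of the combination are to be tracked carefully, so late toxicity matters to this study.

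The start points differ too, so an event between enrollment and the first dose falls inside one window and outside the other.

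**Working it through.** The plan gives no figure for AE capture, so there is none to reproduce. The check is calendar arithmetic and a comparison of passages.

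**Inputs**
- Footnote window: 90 days after the last vismodegib dose (Table 6.1).
- Abstract and 7.4 window: 12 months after the last study treatment.
- End of Treatment visit: 8 to 12 weeks, so days 56 to 84 after the last dose (6.1.3).
- Follow-up visits: 3, 6 and 12 months after that visit, plus or minus 14 days (6.1.4).
- Conventions: 12 months = 365 days, 6 months = 183, 3 months = 91. Day 0 is the last dose, assumed to be also the day of the last radiation fraction.

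**Step 1. Days the footnote leaves out.** 365 − 90 = 275 days (days 91 to 365), and 275/365 = 75%. The fourth stage begins when the first 3 months end, so essentially all of it lies beyond day 90.

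**Step 2. Where the visits fall.**

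| Visit | Earliest day | Latest day | Within 90 days? | Within 365 days? |
|---|---|---|---|---|
| End of Treatment | 56 | 84 | yes | yes |
| 3 months | 56 + 91 − 14 = 133 | 84 + 91 + 14 = 189 | no | yes |
| 6 months | 56 + 183 − 14 = 225 | 84 + 183 + 14 = 281 | no | yes |
| 12 months | 56 + 365 − 14 = 407 | 84 + 365 + 14 = 463 | no | no |

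Every follow-up visit is after day 90. The 12-month visit is also after day 365, because visits are counted from End of Treatment and the window from the last treatment.

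**Step 3. Which outputs depend on the choice.**

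| Output | Footnote followed | 7.4 followed |
|---|---|---|
| On-treatment stages and interim safety rule (8.4) | complete | complete |
| First 3 months after therapy | essentially complete if drug and radiation end together | complete |
| New events, 3 to 12 months after therapy | not required | complete |
| Events already ongoing | followed under the footnote | followed |
| Primary endpoint | not affected | not affected |

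**Step 4. Direction of the error.** Let p be the true proportion of patients with a new event in the fourth stage, and f the share of patients at sites that apply the footnote. Suppose those sites report none of these events, the others report all of them, and p is the same everywhere. The expected reported proportion is then p(1 − f). It equals p when f = 0 and falls to 0 when f = 1, so the error is never upward. The documents give no value for f.

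**Step 5. Grade.** A site that enters all AEs under 7.8 also satisfies 7.6 and Appendix 9, which set a minimum. If a site instead reads 7.6 and the back-reference in 7.8 as a limit, three things would be incomplete in the database: the all-AE counts and attributions, the percentage of patients with any AE, and the grade 1-2 cells of the maximum-grade tables. Outputs for grade 3 or higher and grade 4-5 would not change.

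**The case against.** The best defence is that the Abstract and 7.4 agree, that 7.4 is the section governing safety evaluation, and that AE assessment is scheduled at every follow-up visit. Late events would then be seen at visits, and a site following 7.4 would report them. This stands as a limit on size: the loss may be zero, and 275 days is a per-patient maximum. It is smaller still where follow-up visits stop at progression or the window closes at discontinuation. A site could also apply 7.4's rule for later attributed SAEs once the footnote's period ends, which would save those SAEs but not other new events. None of this says which window governs, and the footnote is attached to the AE row itself.

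Three stronger readings are tempting, and the documents do not support them.

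- *Grade 1-2 events are not collected, so the all-grade outputs cannot be produced.* Section 7.6 has the investigator grade and record events on a scale that defines grades 1 and 2. Section 7.4 makes the Study Chair responsible for ensuring that "all AEs and SAEs that are observed or reported during the study, are collected and reported". Section 7.9 forwards all non-serious AEs quarterly. At worst, grade 1-2 data would have to be retrieved from source.
- *Counting from the drug alone also cuts into the first 3 months after therapy.* That could happen if the drug ended before radiation. But 5.3 has drug days made up after an interruption, so the last dose could equally follow the last fraction. The effect has no fixed direction and the documents give no rate for it.
- *Only drug-related events are reported.* Section 7.4 does describe safety assessment as "monitoring and reporting adverse events (AEs) and serious adverse events (SAEs) that are considered related to vismodegib", but the same section requires all AEs to be reported.

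**Conclusion.** The window contradiction is real, stands in current text and should be corrected. If the footnote is followed, new events with onset on days 91 to 365, including grade 3 or higher, need not be reported. That is up to 275 of 365 days (75%) per patient and essentially the whole fourth stage; if 7.4 is followed, it is 0. With mixed practice, the 3-to-12-month toxicity proportions would be unreliable and biased low, by an amount the documents do not allow one to estimate. The day counts assume that drug and radiation end together and that the patient stays in follow-up for the full year. The difference in start points is a second, smaller conflict in the same rule.

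The OnCore grade wording needs clarification only: it puts the all-grade summaries at risk of being incomplete in the database, not beyond recovery.

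**What to change.** 1. In the Table 6.1 footnote, adopt the end point of the Abstract and 7.4: 12 months after the last protocol treatment (drug or radiation, whichever is later), or study discontinuation or termination if earlier.
2. State one start point in the Abstract, the footnote and 7.4. Keep the footnote's rule for screening SAEs and its follow-up of ongoing events.
3. State that the 12-month visit, which falls after day 365, records events with onset up to the end of the window.
4. In 7.6 and 7.8, state that AEs of all grades are entered in OnCore, with grade 3 to 5 as the subset for committee review. Appendix 9 does not exclude lower grades and need not be amended.

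The toxicity stages in 8.2 and 8.5 can stay as they are. The cost is a short wording amendment and some extra data entry at visits where AE assessment is already scheduled.
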